5.3 Strategies for Recruitment and Retention

Subjects will be recruited from two main sources:

1. Subjects will be recruited from the PI's clinical practice, which specializes in patients with low vision related to neurological conditions. Several ophthalmologists, neurologists, and physiatrists in the MGB system are aware of the PI's expertise in severe neuro and myogenic ptosis and associated strabismus, and routinely refer their patients to the PI's clinic where they will be offered participation if appropriate. Subjects recruited from the PI's clinic will be contacted by telephone, email or letter with brief details about the study (see attached telephone script and email/letter script). For participants who are among the investigator's own patients, the risks of coercion or undue influence will be minimized by having a study team member other than the PI contact the patient about the study.
2. Subjects will be recruited from other relevant clinics within the MGB network (e.g., the MGH neuromuscular clinic). Non-study staff physicians at MEEI and other local Boston

area practices within the MGB network will be sent a letter (see uploaded practitioner's letter) asking them to provide approved study recruitment flyer (see uploaded flyer) to potential participants. The flyer includes contact information so the participant can directly contact a member of the study team. In addition, flyers may also be posted in public areas in clinics, when permitted.

We do not anticipate any problems with subject retention. Typically patients are eager to participate because we are providing treatments that may improve eye opening. Subjects will receive regular follow ups which will help facilitate retention. Participants will receive remuneration for participating in this research study. They will receive \$60 at the end of the second period of the crossover (typically visit 6). This will be done using a Clin*i*Card.

5.4 Participant Withdrawal or termination

5.4.1 Reasons for Withdrawal or Termination

Subjects have a right to withdraw from the study at any time. Additionally, the subject may be withdrawn from the study for any reasons: if it is in the best interest of the subject, intercurrent illness, adverse events, or worsening condition. The site investigators may request the withdrawal of a subject because of protocol violations, administrative reasons, or any other valid and ethical reasons.

Reasons for subject discontinuation may include, but are not limited to, the following:

1. Investigator determination that it is not in the best interest of the subject to continue participation
2. Serious adverse events
3. Any other safety concerns

5.4.2 Handling of Participant Withdrawals or termination

If a participant needs to withdraw early, they will be asked to accept a final telephone call at the end of the study to confirm vital status. Participants who are withdrawn due to an adverse event, serious or not, will be followed until the resolution of the event.

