5.5 Premature Termination or Suspension of Study

If the study is terminated or suspended prematurely, all enrolled participants will be notified and asked to attend a final safety visit. If there are participants with ongoing adverse events at the time of premature termination those participants will be followed until resolution of the event.

6 STUDY Device

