7.3.6 Early Termination Visit

In the event a participant is terminated from the study due to an Adverse Event, the study PI will follow the participant for at least 30 days after termination to confirm the event has resolved or the patient is receiving appropriate treatment.

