10.5 Sample Size

Sample size was estimated based on available preliminary data at the time of study planning, estimating 40 would need to complete the crossover with an estimated attrition of 10 giving a total of 50 planned for enrollment. However, this was able to be greatly reduced given the size of the effects measured in the interim analyses conducted after 8 participants had completed the crossover. The final sample size required to measure the primary outcome with power of 0.80 and type II error of alpha 0.05 was 16.

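### A participant who withdraws early without a recorded adverse event has no planned exit check of cornea or lid skin

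*Combined protocol and SAP*

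**What the plan says.** Four parts of the protocol deal with leaving early.

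- **5.4.2, any early withdrawal:** "If a participant needs to withdraw early, they will be asked to accept a final telephone call at the end of the study to confirm"; what the call confirms is vital status.
- **5.4.2, withdrawal because of an adverse event:** "Participants who are withdrawn due to an adverse event, serious or not, will be followed until the resolution of the event".
- **7.3.6, headed as an early termination visit:** it opens "In the event a participant is terminated from the study due to an Adverse Event" and says that "the study PI will follow the participant for at least 30 days after termination". It makes no provision for other withdrawals.
- **5.5, whole study stopped:** "all enrolled participants will be notified and asked to attend a final safety visit".

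The schedule in 7.3.7 has rows for Visits 1 to 8 and the telephone contacts, and none for an exit or early termination visit. Section 8.1 assesses safety at visits. It bases ocular safety on ophthalmic examination and spontaneous reports, and names related corneal ulcer and broken eyelid skin as grounds for immediate dismissal. On expected losses, 10.5 gives "estimating 40 would need to complete the crossover with an estimated attrition of 10 giving a total of 50 planned for enrollment".

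**The concern.** The harms that the protocol names are reduced blink, surface drying, discomfort, skin irritation, corneal ulcer and broken lid skin. A vital-status call at the end of the study measures none of them. In each period the home-wear week falls between the second training visit and Visit 3 or Visit 6, which carries the post-wear slit lamp, NEI grading and skin rating. Someone who withdraws during that week without a recorded adverse event misses that examination, and nothing replaces it.

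Two things are at stake. A participant may leave with a corneal or skin change that nobody has seen. And the examination part of the ocular safety outcome is missing for that participant, in a trial whose final sample size is 16.

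**Working it through.** **Step 1. Contact planned for each way of leaving**

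| Situation | Planned contact | Cornea or lid skin examined? |
|---|---|---|
| Adverse-event withdrawal (5.4.2, 7.3.6) | Followed to resolution; at least 30 days | Implied by follow-up of the event |
| Whole study stopped (5.5) | Final safety visit for all | Implied by the visit's purpose |
| Other early withdrawal (5.4.2) | Vital-status call at end of study | No |
| Calls at 6 and 12 months (7.3.5, 7.3.7) | Questionnaires, timed from the final study visit | No |

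The third row is the gap. The fourth does not fill it, even if withdrawn participants are meant to be among those called. Section 5.4.1 lists worsening condition and other safety concerns separately from adverse events, so a safety-related withdrawal can fall in the third row.

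**Step 2. What already narrows it**

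- An adverse event under 8.1.1 includes any symptom, related or not. The investigator classifies it (8.2), and 10.4.7.1 gives mild lid discomfort as an example of a minor event to be recorded. A withdrawal for discomfort that staff know about therefore belongs in the first row.
- During home wear there is a video call every other day (7.3.2). Under 7.1.1, remote safety checks cover acuity, comfort, the external eye and the lid skin. They do not include slit lamp or NEI grading.
- The text on Risk 2 (reduced blink reflex) tells MLP users with comfort below 5 to remove the device and arrange a visit. The KTFS risk text promises instructions but states no such threshold.
- A participant who leaves in the washout, after Visit 3, has already had the post-wear examination for the first device.

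The remainder is change that is unreported or causes no symptoms and arises after the last examination. Exclusion 5 in section 5.2 admits participants with reduced corneal sensation if a specialist clears them; discomfort may be an unreliable signal in that group.

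**Step 3. How many could be affected**

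Inputs from 10.5: 40 completers, attrition of 10, enrolment of 50. Attrition is 10/50 = 20%, and 40/(1 − 0.20) = 50 reproduces the plan's figure. If 20% still applies and the final 16 means completers (10.5 states neither), enrolment is 16/0.80 = 20, with 4 leavers. Treating every leaver as a non-adverse-event withdrawal makes 20% an upper limit at the planned attrition. It refers to the crossover and does not cover losses during extended wear.

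**Step 4. Illustrations only**

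Let c be completers, w leavers, and m the assumed ratio of event risk in leavers to that in completers. The share of events falling among leavers is w·m/(c + w·m). With c = 16 and w = 4:

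- m = 1: 4/20 = 20%
- m = 2: 8/24 = 33%
- m = 3: 12/28 = 43%

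The documents give no value of m, and some of these events would be detected before the participant left.

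There is also a loss of information. With no events seen, the one-sided 95% upper bound on the event rate is 1 − 0.05^(1/n). This is 17.1% for n = 16 and 13.9% for n = 20, the latter if leavers were examined and also had none. For the original plan the values are 7.2% (n = 40) and 5.8% (n = 50).

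**The case against.** The strongest reply is that the protocol already catches the cases that matter. Its adverse-event definition is broad, the investigator rather than the participant decides what counts, and adverse-event withdrawals are followed to resolution. Lid skin, comfort and acuity are checked by video during home wear, so at withdrawal the last check should be about two days old. Most of this stands, and it confines the gap to what Step 2 leaves over. It does not close the gap: no examination is planned after withdrawal, and the video check described for ordinary participants includes no corneal grading.

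A reader might infer three stronger conclusions that the documents do not support.

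- **That these leavers are the participants most likely to be harmed.** The group most clearly at risk, adverse-event withdrawals, is the group that is followed. Nothing in the documents ranks the rest.
- **That leavers will be counted as event-free or dropped, so that incidence is understated, most of all for the less tolerable device.** No section says so. Section 8.1 defines safety by event incidence during the study without a completers-only denominator, and 10.4.5 has withdrawals and safety issues summarised for the safety monitor.
- **That the understatement can be given a number.** It depends on invented rates. With events in 10% of 16 completers and 50% of 4 leavers, incidence is (1.6 + 2.0)/20 = 18%, against 1.6/16 = 10% in completers, or 1.6/20 = 8% if leavers count as event-free. With 20% in leavers it is (1.6 + 0.8)/20 = 12%. With 10% in both groups it is 2.0/20 = 10%, and the completers-only figure has no bias.

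**Conclusion.** The concern holds in a limited form. For early withdrawal without a recorded adverse event, the plan schedules no check of cornea or lid skin, and its one contact asks about something else. This is out of line with 5.5, which provides a safety visit when the whole study stops. The gap is mainly unreported or asymptomatic corneal or skin change after the last examination.

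At the planned attrition, at most 20% of participants in the crossover are affected. The true share is lower to the extent that withdrawals are for recorded adverse events or follow a completed post-wear visit. The direction and size of any bias in the event rates cannot be derived from the documents. This is a cheap improvement to the plan and does not show that the safety result will be wrong.

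**What to change.** Reconcile 5.4.2 and 7.3.6 with 5.5, and add an exit row to 7.3.7:

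1. Offer any participant who withdraws after a device has been applied the existing Visit 3/6 safety assessments soon after withdrawal: acuity, slit lamp with NEI grading, skin rating and comfort. Do this in person, or by video where the remote cornea supplies were provided. Section 7.10 describes the Burton lamp and fluorescein strips only for remote enrollees (up to 10), so for others a video check would not replace the corneal examination.
2. If the participant declines, make the telephone call at the time of withdrawal. Ask about eye and skin symptoms and the reason for stopping.
3. State that everyone to whom a device was applied is in the safety denominator.

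The cost is one earlier visit or call per leaver, using assessments already in the schedule. Some leavers will decline, which remains their right under 5.4.1, and the reported event rate may rise slightly.

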5.5 Premature Termination or Suspension of Study

If the study is terminated or suspended prematurely, all enrolled participants will be notified and asked to attend a final safety visit. If there are participants with ongoing adverse events at the time of premature termination those participants will be followed until resolution of the event.

6 STUDY Device

6.1 Study Device Description

Magnetic Levator Prosthesis (MLP):

Neodymium magnet embedded in a glasses frame and a polymer embedded (PDMS) micro-magnet array fitted externally to the upper lid with IV 3000 securement film. The IV 3000 is FDA approved for extended wear on the skin. Tegaderm, which is essentially the same adhesive, is even FDA approved as an eye covering (we used Tegaderm in early studies but switched to IV 3000 for its superior ease of handling based on packaging technique). It generates a strong bond, in a prior study keeping the magnetic array affixed to the eye lid skin for a mean of 6 ± 4 days with good participant reported comfort when used for

Clinical Trial to improve the magnetic levator prosthesis (MLP) including the development and testing of a novel adjustable force system and comparison to the Kinesio Tape frontalis sling (KTFS) Version 1

2 hours per day during rehabilitation therapies. In order to allow doctors and patients to easily adjust the force of the MLP in the interest of maximizing their comfort and blink quality while accommodating variability in ptosis or lid magnet positioning, we propose to further develop and test a novel approach where the force is adjusted by manually rotating the spectacle magnet with a small dial on the side of the spectacle frame. The MLP is FDA exempt as a Class 1 Device. An Investigational Device Exemption (IDE) application was not required in prior studies approved by the MEEI IRB HSC and should not be required in order to carry out this study. MLP status as a device was reviewed extensively by [name] and her team as well as by legal ([name]), last reviewed in fall 2017.

Kinesio Tape Frontalis Sling (KTFS):

Kinesio Tape is FDA registered as a 510K exempt class 1 device, typically used by physical and occupational therapists to support muscular healing and movement. It is sometimes used on the face in cases of facial palsy or on the eye lid to support the lid in cases of severe blepharoptosis. In such cases it may be attached near the lid margin above the lashes extending up to the forehead skin overlying the frontalis muscle. Alternatively it may be a very short piece attached only along the lid skin. The tape is easily removed.

6.1.1 Acquisition

Magnets will be acquired from SM Magnetics, Pelham AL or similar supplier. PDMS supplies will be acquired from Fisher Scientific. Frame supplies will be acquired from Designs For Vision Rokokam, NY, Michelle Moretti Eyeware and Skelmet, Boston MA. Kinesiotape will be acquired from Kinesio Holding Corporation, Albuquerque, NM.

6.1.2 Formulation, Appearance, Packaging, and Labeling

Arrays will be labeled with lot and batch numbers.

6.1.3 Product Storage and Stability

Only the arrays have an expiration date. Neodymium magnets are highly stable and resistant to demagnetization. The spectacle magnets will have an expiration of 5 years. The PDMS arrays will have an expiration of 1 year. They are stored at room temperature.

6.1.4 Preparation

Magnets are prepared by the manufacturer and coated in nickel. They will be embedded in PDMS at Schepens Eye Research Institute using a mold produced onsite with a 3-D printer.

6.1.9 Duration of Therapy

see other sections

6.1.10 Device Specific Considerations

The MLP is FDA exempt as a Class 1 Device and therefore an Investigational Device Exemption (IDE) application was not required in prior studies approved by the MEEI IRB HSC and should not be required in order to carry out this study. MLP status as a device was reviewed extensively in the fall of 2017 by [name] and her team as well as by legal ([name]). Mass Eye and Ear has submitted a patent application for the technology, and so status was also reviewed by [name] and his team in the Intellectual Property department.

Kinesio Tape is FDA registered as a 510K exempt class 1 device, typically used by physical and occupational therapists to support muscular healing and movement. It is currently used as a treatment to support the lid in cases of severe blepharoptosis. As such an IDE should not be required.

6.2 Study agent Accountability Procedures

The devices will be stored in the lab offices at Schepens Eye Institute and dispensed at Massachusetts Eye and Ear in the vision rehabilitation service clinical research lab (8th floor, [name]). Logs will be kept by the Research Assistant and Engineering Research Fellow to keep account of which devices were used for the specific subjects. If devices are returned that will also be noted on the device logs.

7 STUDY PROCEDURES AND SCHEDULE

7.1 Study Procedures/Evaluations

7.1.1 Study specific procedures

The following procedures will be performed as part of the study (see schedule of events table in section 7.3.7.)

1. Refraction (if needed)
2. Visual acuity
3. Slit lamp examination of external eye, lid and cornea with Nafl & NEI scale
4. Comfort rating
5. Video recording of eye blinks
6. Rating of skin integrity
7. EQ-5D-5L questionnaire
8. GBI questionnaire
9. aQoL questionnaire

Based on experience, we anticipate that the first study visit will typically last about 120 minutes and subsequent visits about 60 minutes.

Some of the visits will be conducted virtually (as detailed in subsequent sections). To facilitate virtual visits, a visual acuity chart will be given to the subject to allow this safety outcome monitoring remotely and other safety outcomes will be conducted during the call (comfort scale, inspection of the external eye and lid skin).

Detailed plan for REDCap text message and email communication:

A short three-question survey will be used to document whether subjects are wearing a device during the periods of home use. Consent to receive a survey link by text message or email will be documented in the consent form along with the preferred contact method (text, email, or both). For subjects that consent to receive the survey links, their preferred phone number and/or email address will be recorded on a sheet separate from the consent form, which will be kept in a locked cabinet in a locked office. As soon as the phone number and/or email address have been input into REDCap, the original will be shredded.

Subjects who consent to receive the survey links will receive a text message or email (based on their communication preference) with a link to a REDCap survey twice daily when using one of the devices at home during the trial week. Please see uploaded document for details of the survey language and questions. Subjects will be able to decline receiving the survey links at any time.

Text message plan: Text messages will be sent to subjects using the Twilio platform. The “Survey as webpage” option will be selected so that subjects can access the REDCap survey URL directly from the text. Subjects’ phone numbers will only be entered if they consented to receiving messages in this way. A sentence in the text message will notify the subject that they can opt out of receiving these texts by replying “Stop”.

Email plan: In the event that subjects prefer to be contacted by email, they will receive the link to survey sent to their email through the REDCap platform. The “automated invitations” option will be used to send out emails at certain times of day to the subjects. Subjects’ emails will only be entered if they consented to receiving messages in this way. A sentence in the email message will notify the subject that they can opt out of receiving these emails by replying “Stop”.

7.3 Study Schedule

The study schedule is summarized below (section 7.3.7).

7.3.1 Screening

Pre-Screening: In order to guide the consent/assent process, the approved study staff will administer a pre-consent cognitive screening using the Mini-Mental State Exam (MMSE). If score is 18-23 (maximum of 30) representing mild cognitive impairment (Tombaugh et al 1992), candidates will be asked to return with a caregiver (if one is not present). If score is <18, they will not be eligible.

Screening: Subjects with MMSE scores of at least 18 will undergo consent procedures at the start of the first visit. After consent, the eligibility check list (uploaded) will be used to determine eligibility. Only eligible subjects will be enrolled in the clinical trial.

7.3.2 CROSSOVER

After consent and enrollment, subjects will be randomly assigned to one of the two arms for the crossover period. In one arm subjects will receive the MLP first and the KTFS second. In the other arm, subjects will receive the KTFS first and the MLP second.

Each period of the crossover will last for about three weeks, including about two weeks of training in how to apply and remove the device followed by about one week of using the device at home. Training will be conducted at study visits at Mass Eye and Ear. Typically there will be two training visits. Baseline measures of eye lid blinking without and with the device will be taken during training. For the MLP, two baseline measures of eye lid blinking will be recorded one with the real MLP device and one with a sham MLP device to determine how much improvement might occur simply through a placebo effect. However, for the KTFS it will not be possible to take a baseline measure with a sham KTFS. Only subjects and caregivers who demonstrate sufficient ability to apply and remove the device will be permitted to take it home. During the period of home wear, there will be a video call every other day to monitor the subject’s use of the device and safety. During the kfts arm, an occupational or physical therapist consulting with the Massachusetts eye and ear study team may talk with the subject during the video conference call to ensure that the kinesio tape is in the correct position. Mass General Brigham approved software will be used for video calls. During the trial week of home use of devices, subjects will

also receive REDCap survey link notifications each day to complete a brief survey to log if they are wearing the device (see the detailed plan above, and see attached document for survey language and questions).

To ensure no carry-over effects, there will be a washout of about 2 weeks duration between the first and second period of the crossover during which subjects will not be permitted to use any device for their blepharoptosis. (This will be similar to their habitual state before enrollment since none of the participants would have been using any device for their blepharoptosis about two weeks before enrollment).

At the end of the second period of the crossover, subjects will receive a phone call at which the comparison questionnaire (comparing the two devices) and the debriefing questionnaire will be administered. Subjects who express a preference for one of the devices and are interested in continuing to use the preferred device will be asked to attend Mass Eye and Ear for a study visit with [name] determine whether it is clinically appropriate for them to continue with the preferred device. Subjects who do not wish to continue with either of the devices will have no further in-person study visits after this point (but will be asked to complete the 6 and 12 month telephone follow ups), and they will be asked to return the study device unless they get special approval from the clinic to keep it as part of their continued treatment.

